5.2.3. Data Collected from Withdrawn Subjects

In the case of subject withdrawal, the appropriate disposition CRF page will be completed for Treatment or Follow-Up, as applicable.

Every attempt should be made to collect follow-up information. The reason for withdrawal from the study will be recorded in the source documents and on the appropriate page of the CRF.

Before a subject is identified as lost-to-follow up, the site should make all reasonable efforts to contact the subject. These attempts must be documented and should include at a minimum one phone call and one certified letter.

In the event that a subject is withdrawn from the study at any time due to an AE or SAE, the procedures stated in [Section 9.2](#) (AE) or [Section 9.4](#) (SAE) must be followed.

5.3. STUDY STOPPING CRITERIA

[REDACTED]

[REDACTED]

- [REDACTED]
[REDACTED]
- [REDACTED]
[REDACTED]
- [REDACTED]
[REDACTED]
- [REDACTED]
[REDACTED]

[REDACTED]

[REDACTED]

[REDACTED]

[REDACTED]

[REDACTED]

[REDACTED]

6.1. 2X-121

[figure not shown]
Subjects will receive twice daily oral administration of 2X-121 monotherapy in Part 1 of the study.

Dose Cohort	2X-121 Monotherapy Dose (BID)
Cohort 1	600 mg (morning dose: 200 mg + evening dose: 400 mg)
Cohort 2	800 mg (morning dose: 400 mg + evening dose: 400 mg)
Cohort 3	1000 mg (morning dose: 400 mg + evening dose: 600 mg)

Study treatment will be labeled, according to the regulatory guidelines, as an investigational product to ensure that it will not be used outside of the clinical investigation. The Sponsor, protocol number, expiry date and time, and any additional relevant information will appear on the pack label.

All study treatment materials will be stored in their original packaging in a safe and secure location at the investigational site. Study treatment material will be disposed of in accordance with institutional and /or local requirements.

[illegible]

6.2. DOVITINIB

Dovitinib (TKI258), a pan-TKI, is an inhibitor of type III-V receptor tyrosine kinases (RTKs) that mediate both endothelial and tumor cell proliferation and survival. Dovitinib is formulated as a film-coated tablet of 100 mg strength.

Subjects will receive daily oral administration of dovitinib in combination with 2X-121 in Part 2 of the study.

Dose Cohort	Combination 2X-121 (BID administration) and Dovitinib
Cohort 1	2X-121 (MTD) + 300 mg dovitinib
Cohort 2	2X-121 (MTD) + 400 mg dovitinib
Cohort 3	2X-121 (MTD) + 500 mg dovitinib

6.2.1. Packaging and Labeling

[REDACTED]

Study treatment will be labeled, according to the regulatory guidelines, as an investigational product to ensure that it will not be used outside of the clinical investigation. The Sponsor, protocol number, expiry date and time, and any additional relevant information will appear on the pack label.

6.2.2. Storage and Handling

[REDACTED]

All study treatment materials will be stored in their original packaging in a safe and secure location at the investigational site. Study treatment material will be disposed of in accordance with institutional and /or local requirements.

6.2.3. Drug Interactions

[REDACTED]

6.3. ADMINISTRATION

6.3.1. 2X-121

[figure not shown]
[figure not shown]
A twice daily dose of 2X-121 will be administered as hard gelatin capsules, independent of food intake in a 28 days cycle. The capsules are to be administered twice a day about the same time each treatment day. In Part 2 of the study, the 2X-121 morning dose will be administered at the same time as dovitinib.

6.3.2. Dovitinib

[figure not shown]
Dovitinib will be administered once daily (morning) on a 5 days on/2 days off schedule independent of food intake at the same time as the 2X-121 morning dose. In a 28 day cycle, dovitinib will be administered C1D1 - C1D5, C1D8 - C1D12, C1D15 - C1D19, and C1D22 - C1D26.

[figure not shown]
6.3.3. Toxicity Management

[figure not shown]
[REDACTED]

6.4. PRODUCT ORDERING

Investigational products will be provided to the investigational site by the sponsor for the duration of the study.

6.4.1. Product Disposition

All drug supplies are to be used only for this protocol and not for any other purpose. The investigator must not destroy any drug labels or any partially used or unused drug supply until instructed by the Sponsor. At the conclusion of the study and as appropriate during the course of the study, the investigator will return all used and unused drug containers and drug labels to the drug distributor as directed by the Sponsor.

6.4.2. Product Accountability

The Investigator or designee will verify the contents of each shipment against the shipping documents. Verification of IP receipt will be documented according to the Sponsor's requirements.

An accountability log will be provided to the site for use by the Investigator to maintain current and accurate inventory records (batch, expiry, and quantity) covering the dispensing and the destruction of the IP.

At the conclusion of the study the Investigator must return or destroy all IP as instructed by the

Sponsor. Further details will be provided in the Pharmacy Manual.

6.5. CONCOMITANT MEDICATIONS

6.5.1. Prohibited Medications and Therapies

- [REDACTED]
- [REDACTED]
 - [REDACTED]
[REDACTED]
 - [REDACTED]
[REDACTED]
 - [REDACTED]
[REDACTED]
[REDACTED]
[REDACTED]
[REDACTED]
 - [REDACTED]
[REDACTED]

6.5.2. Allowable Medications and Therapies

The following medications and therapies are allowed during the study, if in the judgment of the Investigator, they are required for proper care of the study subject:

- Other medications/therapies that are not otherwise prohibited and, in the judgment of the Investigator, are required for proper medical care.

7. DESCRIPTION OF PROTOCOL ASSESSMENTS AND PROCEDURES

7.1. INFORMED CONSENT

A written informed consent will be obtained for this study by the Investigator or designee from all subjects prior to performance of any protocol-specific procedure. This study will be conducted in accordance with the provisions of the Declaration of Helsinki.

The Investigator must comply with applicable regulatory requirements and must adhere to the Good Clinical Practice (GCP) in the process of obtaining and documenting the informed consent. The Investigator, or designee, must also inform subjects of all pertinent aspects of the study. Before written informed consent is obtained from the subject, the Investigator or a person designated by the Investigator, must provide the subject enough time and opportunity to inquire about the details of the study and to decide whether or not to participate in the trial. All questions addressed by the subject about the study must be answered to the satisfaction of the subject. Prior to the subject's participation in the trial, the written informed consent must be signed and personally dated by the subject and by the person who conducted the informed consent discussion. Authorization for release of protected health information must also be obtained, as per local policies.

7.2. ASSESSMENT OF ELIGIBILITY

The Investigator must assess subject's continued eligibility for the study as per the Inclusion and Exclusion criteria, during the Screening Phase. The eligibility criteria are described in [Section 3.4.1](#) (Inclusion Criteria) and [Section 3.4.2](#) (Exclusion Criteria). In the event that the subject is not suitable or eligible for the study, the subject will be considered "screen failure".

7.2.1. Re-screening

A subject who signed a consent form but did not meet the inclusion/exclusion criteria is classified as a screen failure.

Note: If a subject initially fails to meet inclusion/exclusion criteria and is later reconsidered for participation, the subject will be re-consented and assigned a new unique identification number at the time of re-screening. Subjects who fail their first screening attempt may be re-screened a maximum of once and may be enrolled if they are found to meet all inclusion and no exclusion criteria when re-screened.

For consented subjects who do not meet eligibility criteria, a Screen Failure Case Report Form (CRF) will be completed. The Screen Failure CRF will contain the following details: the subject identification number, the date of ICF signature, demographic information (see [Section 7.3](#)), and the reason for screen failure. No additional information will be required for subjects who fail screening.

7.3. DEMOGRAPHIC INFORMATION

In this study the demographic information will include:

- Dates of ICF signature
- Date of birth
- Gender
- Race (American Indian or Alaska Native, Asian, Black or African American, Native Hawaiian or Other Pacific Islander, White, Not Reported, or Unknown)
- Ethnicity (Hispanic or Latino, Not Hispanic or Latino, Not Reported, or Unknown)
- Use of tobacco or nicotine replacement products and e-cigarettes

7.4. MEDICAL HISTORY

A medical history will be recorded during the Screening Phase and will include:

- All ongoing medical conditions
- All previously resolved medical conditions that are relevant in the judgment of the Investigator
- Any prior medical conditions that have resolved within the last year

Events that emerge prior to the first treatment will be recorded in the medical history and not as AEs. Aside from being used to determine subject eligibility, this information will permit the Investigator to record the nature, duration, and severity of any ongoing baseline medical conditions prior to the subject's receiving investigational product treatment.

For each relevant history, the following will be documented:

- Disease/disorder/condition
- Date of diagnosis
- History status (resolved or ongoing).

7.5. PHYSICAL EXAMINATION

The physical examination will include routine examinations for the following:

- Constitutional/General Appearance
- Head, Ears, Eyes, Nose, Throat (HEENT)
- Neurologic

- Cardiovascular
- Musculoskeletal and Extremities
- Dermatologic
- Respiratory
- Gastrointestinal
- Genitourinary
- Lymphatic
- Psychiatric

Each abnormality will be recorded and the Investigator will record an assessment of its clinical significance.

7.6. VITAL SIGNS, HEIGHT AND WEIGHT

The following vital signs will be collected:

- Systolic and Diastolic Blood Pressure
- Heart Rate
- Respiratory Rate
- Oral Temperature

Blood pressure and heart rate will be obtained in the supine position after subject has been resting for 5 minutes.

In addition, the following will be recorded:

- Height (Only performed at Screening visit)
- Weight
- Body Mass Index

7.7. CONCOMITANT MEDICATION

The subject may be applied any medications judged necessary by the Investigator, provided such medications are not listed in [Section 6.5.1](#).

All medications and therapies administered or taken by the subject beginning 30 days prior to Screening Visit and throughout the study will be recorded in the source documents and on the appropriate page of the Case Report Form (CRF). Subjects must be questioned at each study visit

[figure not shown]
concerning any new medications or changes in current medications including over-the-counter medication and topical medication.

For each medication and non-study treatment, the following will be documented:

- Medication/treatment name (generic name may be used if trade name is unknown)
- Dose, unit, and frequency of dosing (individual dosages, not total daily dose).
 - **Note:** *Each new dose of medication should be recorded as a separate entry, with the exception of medications that are given on a sliding scale. For these, it is acceptable to enter the range of the dosage, including the start and stop dates for which the specified dosage range was used.*
- Route of dosing
- Indication for use
- The start date
- The stop date (if medication/therapy is not ongoing).

7.8. CLINICAL LABORATORY ASSESSMENTS

All laboratory assessments will be reviewed by the Investigator. If clinically significant findings, as determined by the Investigator, are recorded for a particular symptom, sign or abnormal measurement, that measurement will be repeated at medically appropriate intervals until the value returns to an acceptable range, a specific diagnosis is established, or the condition is otherwise explained.

[REDACTED]

[REDACTED]

[REDACTED]

[REDACTED]

[REDACTED]

[REDACTED]

[REDACTED]

[REDACTED]

[REDACTED]

[REDACTED]
[REDACTED]
[REDACTED]
[REDACTED]
[REDACTED]

[REDACTED]
[REDACTED]
[REDACTED]
[REDACTED]
[REDACTED]

[REDACTED]
[REDACTED]

[REDACTED]
[REDACTED]

[REDACTED]

[REDACTED]
[REDACTED]
[REDACTED]
[REDACTED]
[REDACTED]

[REDACTED]
[REDACTED]

[REDACTED]

[REDACTED]

[REDACTED]

7.9.1.1.

[REDACTED]

[REDACTED]

[REDACTED]

[REDACTED]

[REDACTED]

[REDACTED]

[REDACTED]

[REDACTED]

[REDACTED]

[REDACTED]

[REDACTED]

[REDACTED]

- [REDACTED]
[REDACTED]
[REDACTED]
- [REDACTED]
[REDACTED]
[REDACTED]
[REDACTED]
- [REDACTED]
 - [REDACTED]
[REDACTED]
[REDACTED]
[REDACTED]
- [REDACTED]
[REDACTED]
[REDACTED]
[REDACTED]
- [REDACTED]
[REDACTED]
- [REDACTED]
[REDACTED]
- [REDACTED]
[REDACTED]
[REDACTED]
- [REDACTED]
[REDACTED]
- [REDACTED]
[REDACTED]
[REDACTED]
[REDACTED]
- [REDACTED]
[REDACTED]
- [REDACTED]
[REDACTED]
[REDACTED]
[REDACTED]
- [REDACTED]
[REDACTED]
- [REDACTED]
[REDACTED]
[REDACTED]
- [REDACTED]
[REDACTED]

[REDACTED]

- [REDACTED]

[REDACTED]

- [REDACTED]

- [REDACTED]

[REDACTED]

[REDACTED]

- [REDACTED]
- [REDACTED]
- [REDACTED]
- [REDACTED]
- [REDACTED]

- [REDACTED]
- [REDACTED]

[REDACTED]

[REDACTED]

[REDACTED]

[REDACTED]

[REDACTED]

[REDACTED]

[REDACTED]

[REDACTED]

[REDACTED]

[REDACTED]

[REDACTED]

[REDACTED]

[REDACTED]

[REDACTED]

[REDACTED]

[figure not shown]
[REDACTED]

[REDACTED]

[REDACTED]

[REDACTED]

[REDACTED]

[REDACTED]

[REDACTED]

[REDACTED]

[REDACTED]

[REDACTED]

[REDACTED]

7.10. 12-LEAD ELECTROCARDIOGRAM

12-Lead ECG will be performed per the site standard procedures. [REDACTED]

[REDACTED]

[REDACTED]
 [REDACTED]
 [REDACTED]
 [REDACTED]
 [REDACTED]
 [REDACTED]
 [REDACTED]

[REDACTED]

[REDACTED]

[REDACTED]

[REDACTED]

[illegible]

[REDACTED] [REDACTED]

8. STATISTICAL CONSIDERATIONS

This section presents general information about statistical considerations and concepts such as randomization, covariates/stratification, statistical power, sample size, and a brief discussion on analysis methodology, as well as some data conventions. Detailed descriptions of the statistical analysis methods and data conventions will be included in a separate document; i.e., the Statistical Analysis Plan (SAP).

8.1. TREATMENT GROUPS

Refer to [Table 4-1](#) and Table 4-2 for description of treatment groups.

8.2. STUDY OUTCOME MEASURES

Refer to [Section 2.2](#) for list of study outcome measures.

8.3. SAMPLE SIZE DETERMINATION AND RATIONALE

A sample size of up to 16 subjects in Part 1 and in up to 24 subjects in Part 2 will be used in this trial. This sample size is selected based on the conventional 3+3 study design and not based on statistical power calculation; it is deemed adequate to provide clinically meaningful descriptive results consistent with study objectives.

8.4. RANDOMIZATION AND STRATIFICATION

Not applicable.

8.5. BLINDING AND PREVENTION OF BIAS

Not applicable.

8.6. INTERIM ANALYSIS

Not applicable.

8.7. GENERAL STATISTICAL CONSIDERATIONS

All collected study data will be presented in subject data listings and/or will be summarized. Statistical analyses will be performed using SAS® for Windows, version 9.4 or later.

A Statistical Analysis Plan (SAP) will be developed and approved before the database is locked. The SAP will present the detailed statistical methodology to be used in analyzing the efficacy and safety data from this trial.

8.7.1. Analysis Populations

8.7.2. Covariates and Subgroups

8.7.3. Missing Data

All efforts will be made to minimize the amount of missing data for the study. The methods of handling missing data will be detailed in the SAP.

8.1. STATISTICAL METHODS

8.1.1. Subject Disposition

The disposition of all subjects who signed an ICF will be provided. The numbers of subjects screened, received treatment, completed, and discontinued during the study, as well as the reasons for discontinuation will be summarized. Disposition and reason for study discontinuation will also be provided as a by-subject listing.

8.1.2. Demographics And Baseline Characteristics Analysis

Demographics and baseline characteristics will be summarized using appropriate descriptive statistics.

8.1.3. Concomitant Medications/Therapies

All prior and concomitant medications recorded in the case report form will be coded to all matching Anatomic Therapeutic Classification codes using the most recent version of the WHO Drug Dictionary. Descriptive summaries will be prepared using the coded term. All concomitant medications recorded in the case report form will be listed.

8.1.4. Efficacy Analyses

All efficacy data collected will be summarized and analyzed according to the variable type:

- [REDACTED]
 - [REDACTED]
 - [REDACTED]
- [REDACTED]
 - [REDACTED]
- [REDACTED]
 - [REDACTED]

8.1.6. Safety Analyses

8.1.6.1. Adverse Events

Adverse events will be classified by System Organ Class (SOC) and Preferred Term (PT) according to the most recent version of MedDRA dictionary.

- [REDACTED]
- [REDACTED]
- [REDACTED]
 - [REDACTED]
 - [REDACTED]
 - [REDACTED]
 - [REDACTED]

8.1.6.2. Clinical Laboratory Data

- [REDACTED]
- [REDACTED]

[REDACTED]

[REDACTED]

8.1.6.3. Vital signs

[REDACTED]

[REDACTED]

[REDACTED]

8.1.6.4. Physical Examination

[REDACTED]

8.1.6.5. ECG

[REDACTED]

[REDACTED]

[REDACTED]

8.1.6.6. Other Safety Data

[REDACTED]

[REDACTED]

9. SAFETY REPORTING

The Investigator is responsible for the detection and documentation of events meeting the criteria and definition of an AE or SAE, as provided in this protocol. During the study when there is a safety evaluation, the Investigator or site staff will be responsible for detecting, documenting, and reporting AEs and SAEs as detailed in this Section of the protocol.

9.1. ADVERSE EVENT (AE) DEFINITION

An adverse event (AE) is defined as any unfavorable or unintended sign, symptom, or disease that occurs or is reported by the patient to have occurred, or a worsening of a pre-existing condition. An adverse event may or may not be related to the study treatment.

AEs will be elicited through direct questioning and subject reports. Any abnormality in physical examination findings or laboratory results that the investigator believes is clinically significant (CS) to the research subject and that occurred after initiation of the first study treatment will be reported as AEs. Abnormal findings that are NOT clinically significant should not be recorded as an AE.

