2.2. STUDY OUTCOME MEASURES

2.2.1. Primary Outcome Measure

The primary outcome measures in this study are:

Part 1

- Determination of the MTD of 2X-121 monotherapy.

Note: The MTD is defined as 1 dose level below the dose in which dose limiting toxicities (DLTs) were observed in $\geq 33\%$ of the participants during the first 14 days of the main treatment period.

Part 2

- Determination of the MTD of dovitinib given in combination with 2X-121 (MTD).

Note: The MTD is defined as 1 dose level below the dose in which dose limiting toxicities (DLTs) were observed in $\geq 33\%$ of the participants during the first 14 days of the main treatment period.

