3. STUDY DESIGN

3.1. GENERAL SCHEMA

This is a Phase Ib, two-part, multi-center study. In Part 1, the study will evaluate the safety and tolerability, antitumor activity, pharmacokinetics, and determine the maximum tolerated dose (MTD) of 2X-121 monotherapy (at BID regimen) in patients with advanced solid tumors. In Part 2, the study will evaluate safety and tolerability, antitumor activity, and pharmacokinetics of 2X-121 (MTD) and dovitinib as combination therapy, and determine the MTD of dovitinib when given in combination with the MTD of 2X-121 determined in Part 1.

Part 1

This part of the study will follow an accelerated titration method followed by a standard “3+3” design to determine the MTD of 2X-121. The MTD is defined as one dose level (cohort) below the dose in which dose limiting toxicities (DLTs) were observed in $\geq 33\%$ of the participants.

The calculation of the sample size for this trial is based on the traditional 3 + 3 dose escalation scheme which is conducted as follows:

- Subjects are treated in cohorts of one (Cohort 1) or three (Cohorts 2-3) subjects, each receiving the same dose. For the assessment of a DLT, subjects are observed for 14 days.
- In Cohort 1, if the one subject does not exhibit a DLT, the next cohort of three subjects will receive the next higher dose (Cohort 2). In Cohort 2, if none of the three subjects exhibits a DLT, the next cohort of three subjects will receive the next higher dose (Cohort 3).
- Otherwise, if at least one subject of a cohort exhibits a DLT, a further cohort of three subjects is treated at the same dose level (cohort) without escalating the dose.
- If exactly one out of the six subjects treated at this dose exhibits a DLT, the trial continues as planned at the next higher dose level (cohort).
- If two or more subjects out of the six subjects treated at this dose exhibit a DLT, the dose escalation stops at that level and the next lower dose is considered as the MTD. When the escalation has stopped, additional subjects will be treated at the MTD to a total of six subjects.

[REDACTED]

[REDACTED]

[REDACTED]

[REDACTED]

[REDACTED]

[REDACTED]

[REDACTED]

[REDACTED]

[REDACTED]

[REDACTED]

[figure not shown]
[REDACTED]

- [REDACTED]
[REDACTED]
- [REDACTED]
[REDACTED]
- [REDACTED]
- [REDACTED]
[REDACTED]
- [REDACTED]
[REDACTED]
- [REDACTED]
[REDACTED]

Part 2

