9.2.2. CTCAE Grade (Intensity) Assessment

The guidelines outlined in CTCAE v5.0 will be used for assessing the intensity of the event. The general guidelines for assessing the AE grade appear below. Full guidelines may be obtained at <http://evs.nci.nih.gov/ftp1/CTCAE>.

Table 9-1: CTCAE v5.0 General Guidelines

Grade	Description
Grade 1	Mild; asymptomatic or mild symptoms; clinical or diagnostic observations only; intervention not indicated.
Grade 2	Moderate; minimal, local or noninvasive intervention indicated; limiting age-appropriate instrumental activities of daily living (ADL)*.
Grade 3	Severe or medically significant but not immediately life-threatening; hospitalization or prolongation of hospitalization indicated; disabling; limiting self-care ADL†.
Grade 4	Life-threatening consequences; urgent intervention indicated.
Grade 5	Death related to AE.

*Instrumental ADL refer to preparing meals, shopping for groceries or clothes, using the telephone, managing money, etc.

†Self-care ADL refer to bathing, dressing and undressing, feeding self, using the toilet, taking medications, and not bedridden.

-Common Terminology Criteria for Adverse Events (CTCAE), v5.0: November 27, 2017

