8.2.1.2 Dose Limiting Toxicity (DLT)

All toxicities will be graded using NCI-CTCAE Version 5.0.

All DLTs will be presented as a by-subject listing and summarize descriptively for both parts of the study.

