8.3.1 Adverse Events

Adverse events will be classified by system organ class (SOC) and preferred term (PT) according to the most recent version of MedDRA dictionary.

TEAE are defined as adverse events with onset date on or after the first treatment. TEAEs will be summarized by treatment group, System Organ Class, and preferred term. [REDACTED]

[REDACTED]

[REDACTED]

[REDACTED]

[REDACTED]

[REDACTED]

[REDACTED]

[REDACTED]

[REDACTED]

[REDACTED]

[REDACTED]

[REDACTED]

All adverse events recorded in the eCRF will be presented as by-subject listings.

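### Protocol 9.1 makes a laboratory abnormality an AE only if the investigator calls it clinically significant, with no CTCAE grade threshold, so a high-grade laboratory toxicity can be absent from the TEAE tables

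*Protocol*

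**What the plan says.** Protocol 9.1 opens with a broad AE definition and then narrows it for test findings. What is reported is an abnormality in physical examination or in "laboratory results that the investigator believes is clinically significant (CS) to the research subject", arising after treatment starts. It closes with a prohibition: "Abnormal findings that are NOT clinically significant should not be recorded as an AE".

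Severity is graded on CTCAE v5.0. In Table 9-1 of Protocol 9.2.2, Grade 1 reads "Mild; asymptomatic or mild symptoms; clinical or diagnostic observations only; intervention not indicated", so the scale covers findings that exist only as test results. SAP 8.2.1.2, on DLTs, states: "All toxicities will be graded using NCI-CTCAE Version 5.0".

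Protocol 9.2 attaches the CTCAE grade, causality and impact on study treatment to each AE record. SAP 8.3.1 says: "TEAE are defined as adverse events with onset date on or after the first treatment". Incidence and severity of TEAEs are a named safety outcome in Protocol 2.2.2.3 and SAP 2.6.5.

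The MTD rests on DLTs. Protocol 2.2.1 says: "The MTD is defined as 1 dose level below the dose in which dose limiting toxicities (DLTs) were observed in" at least 33% of participants. Under Protocol 3.1, "For the assessment of a DLT, subjects are observed for 14 days", and "If two or more subjects out of the six subjects treated at this dose exhibit a DLT, the dose escalation stops at that level".

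**The concern.** The grading scale and the recording rule do not match. CTCAE gives a grade to an asymptomatic laboratory finding. Section 9.1 keeps the same finding out of the AE record whenever one investigator, at one of up to five centers in an open-label trial, regards it as not clinically significant. No visible text sets a grade above which the judgement no longer applies.

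Two things are at stake. The TEAE tables would understate laboratory toxicity, by an amount that varies between investigators. Also, 3+3 decisions turn on single events (0 of 3 against 1 of 3, 1 of 6 against 2 of 6), so if laboratory DLTs passed through the same judgement, one unrecorded event could change an escalation decision. In both cases the rule can only remove events, so any error is towards too little toxicity.

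**Working it through.** **Step 1: follow one laboratory value through the visible text.** Take a Grade 3 laboratory value that the investigator judges not clinically significant.

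| Place | What happens to the value |
|---|---|
| Protocol 7.8 | Reviewed by the investigator; the visible repeat-measurement rule applies only to significant findings |
| Protocol 9.1 | Not to be recorded as an AE |
| Protocol 9.2, 9.2.1, 9.2.3 | No AE record, so no causality and no treatment-impact entry there |
| SAP 8.3.1 | TEAEs are adverse events, so it is not a TEAE |
| SAP 8.3.2 | The result appears in a by-subject laboratory listing |
| Protocol 2.2.2.3 | Contributes to laboratory change from baseline, an outcome separate from TEAEs |

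The gap in the TEAE outcome follows from 9.1 and SAP 8.3.1 alone and needs no redacted text. The value itself is kept. What is lost is its place in the TEAE tables and its attribution.

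**Step 2: test the link to DLTs.** Protocol 3.1 refers in Part 2 to a DLT definition given in Part 1, but that text is blacked out. Protocol 2.2.2.3 lists DLTs, TEAEs and laboratory changes as separate items. SAP 8.2.1.2 grades all toxicities and states no clinical-significance filter. No visible sentence makes a DLT a subset of recorded AEs, and none says that laboratory DLTs are assessed apart from the 9.1 judgement. The link is open either way.

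**Step 3: the plan's own figures.** The planned maxima reproduce from the cohort rules: Part 1 is (1 + 3) + 6 + 6 = 16, and Part 2 is 3 × 6 + 6 = 24. A recording rule changes neither.

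**Step 4: sensitivity illustration, if DLTs were missed.** A three-subject level is passed on 0 of 3, or on 1 of 3 followed by 0 of 3. With true DLT rate p and an assumed uncounted share f, the observed rate is q = p(1 − f), and

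P(pass) = (1 − q)³ + 3q(1 − q)⁵.

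For p = 0.33 and f = 0: 0.67³ + 3 × 0.33 × 0.67⁵ = 0.301 + 0.134 = 0.434 after rounding.

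| Assumed f | q (p = 0.33) | P(pass) | q (p = 0.40) | P(pass) |
|---|---|---|---|---|
| 0 | 0.330 | 0.434 | 0.400 | 0.309 |
| 0.1 | 0.297 | 0.500 | 0.360 | 0.378 |
| 0.2 | 0.264 | 0.570 | 0.320 | 0.454 |
| 0.3 | 0.231 | 0.641 | 0.280 | 0.536 |

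The documents give no value for f, and f = 0 is consistent with them.

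**The case against.** A reader might infer that 9.1 causes DLTs to go uncounted and pushes the MTD upwards. The case against that reading is strong.

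- The DLT criteria are redacted. If they name laboratory grades, a qualifying value is a DLT whatever 9.1 says, and no escalation decision is affected.
- Only DLTs set the MTD. TEAE counts do not.
- The only 2X-121 DLT that the visible text reports is fatigue (Protocol 1.5.3), which is not a laboratory event.
- On the protocol's own scale, Grade 3 is severe or medically significant and Grade 4 is life-threatening. Calling such a result not significant fits poorly with the grade, and that investigators would do so is an assumption.
- SAP 8.2.1.1 has the sponsor determine the MTD with a safety assessment committee, so the site does not decide alone.
- Most of Protocol 7.8, all of Protocol 8.1.6.2 and nearly all of SAP 8.3.2 are blacked out. Laboratory CTCAE grading may be in any of them, so its absence cannot be charged to the plan.

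All of this stands against a claim of biased MTD. It does not close the TEAE gap, which rests on readable text. A laboratory listing or a change-from-baseline table does not supply the causality and treatment-impact entries that 9.2 attaches to AEs. The grade descriptions make a dismissed Grade 3 result less likely, but they do not override the instruction not to record it.

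**Conclusion.** The point holds for the AE record. Section 9.1 leaves the recording of laboratory abnormalities to investigator judgement, with no visible grade threshold. A high-grade value judged not significant is therefore absent from TEAE incidence and severity and has no causality or treatment-impact record. The documents give no basis for saying how often this would happen.

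For DLTs, the finding is only that the visible text does not state that laboratory DLTs are assessed independently of the 9.1 judgement. A missed DLT or a biased MTD is possible but not shown. The rise from 43% to between 50% and 64% at a true rate of 33% shows how sensitive a 3+3 level would be if 10% to 30% of DLTs were lost. Those shares are assumptions, and the figures do not estimate what will happen in this trial.

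This is a cheap improvement to the plan.

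**What to change.** 1. Add to Protocol 9.1: any laboratory result that meets a DLT criterion, is CTCAE Grade 3 or higher, or leads to a change of study drug is recorded as an AE regardless of the clinical-significance assessment.
2. State in the protocol that laboratory DLTs are assessed from CTCAE grade, independently of that assessment. If the redacted DLT text already says so, a cross-reference from 9.1 is enough. The statement should not sit in the SAP alone: Protocol 8.7 requires SAP approval only before database lock, so the SAP cannot be relied on to govern escalation.
3. If the redacted parts of SAP 8.3.2 do not already do so, summarise laboratory results by CTCAE grade.

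These are recording and reporting rules. They do not touch the DLT criteria, the doses or the management of any event. The cost is two protocol sentences, a laboratory-grading program on data already collected if none is planned, and a few more AE entries. The maxima of 16 and 24 subjects stay as they are.
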